3.4.2 Exclusion Criteria

Exclusion Criteria

1. Pregnancy
2. Type 1/Type 2 diabetes
3. Chronic medical conditions or medication use that can affect growth, nutrition, blood glucose, insulin secretion, or thyroid function (such as lithium or certain seizure medications)
4. Current use of levothyroxine or anti-thyroid hormone
5. Cyanotic congenital heart disease, or pulmonary hypertension (as described by last echo report in subjects with CHD), or congenital heart disease considered medically unstable by the study cardiologists

Subjects that do not meet all of the enrollment criteria may not be enrolled. Any violations of these criteria must be reported in accordance with IRB Policies and Procedures.

4 STUDY PROCEDURES

4.1 Screening Phase

4.1.1 Telephone screening and medical record review

A telephone screening and medical record review will be done to assess eligibility for the study.

4.2 Observation Phase

4.2.1 Study Visit #1 (0 Month), Blood Draw Visit A (3 Month) & Study Visit #2 (6 Month)

The purpose of the 3 Observation Phase visits is to observe TSH and T4 levels over a period of 6 months. All subjects will get a blood draw for TSH and T4 labs 3 months after the Study Visit #1. The TSH and T4 at 0 and 6 months will be done as part of Study Visit #1 and #2. At the PI's discretion, additional blood draws following the 0 and 6 month visits may take place to assess TSH levels.

The following visits and procedures occur during the Observation Phase:

Study Visit #1 (0 month) = 1 visit lasting approximately 4.5 hours

- Informed Consent: 30 minutes/as long as needed for parent/guardian/participant to fully comprehend the study involvement
- Fasting blood draw: 15 minutes
- Pubertal Status Exam: 5 minutes
- Vital Signs: 10 minutes
- DXA scan: 10 minutes
- Anthropometric measurements: 15 minutes
- PWV and PWA: 30 minutes
- Echocardiography: 20 minutes
- Family history: 10 minutes
- Questionnaire assessments (PedsQL, IWQOL, BES, FRS, ASAQ, CEBQ, CFQ, ABAS-II, HFI): 1.5 hours, or as long as needed by subject and parent/guardian. HFI will be mailed to family and completed prior to visit.
- Physical activity armband (worn at home for 7 days)
- 3 day dietary recalls over the phone from home = Approximately 30 minutes for each diet recall.

Blood Draw Visit A (3 month) = Approximately 15 minutes for blood draw

- TSH & T4 blood draw: 15 minutes

Study Visit #2 (6 month) = 1 visit lasting approximately 4 hours

- Fasting blood draw: 15 minutes
-

-
- Pubertal Status Exam: 5 minutes
 - Vital Signs: 10 minutes
 - DXA scan: 10 minutes
 - Anthropometric measurements: 15 minutes
 - Family history: 10 minutes
 - Questionnaire assessments (PedsQL, IWQOL, BES, FRS, ASAQ, CEBQ, CFQ, ABAS-II, HFI): 1.5 hours, or as long as needed by subject and parent/guardian. HFI will be mailed to family and completed prior to visit.
 - Physical activity armband (worn at home for 7 days)
 - 3 day dietary recalls over the phone from home = Approximately 30 minutes for each diet recall.

4.3 Treatment Phase

4.3.1 Randomization

After Study Visit #2 (6 months), only subjects with persistently elevated TSH (5-10 mIU/mL) will be randomized into two groups of 10. Randomization will be performed centrally by the project statisticians and implemented using opaque sealed envelopes to ensure allocation concealment. Balance between treatment arms will be maintained by use of randomly permuted blocks with unequal block sizes and with stratification by patient gender (two strata, male and female) and age (two strata, ages 8-14 and ages 14-20). After envelopes are opened, treatment assignment will be blinded to the subjects and their parents/guardians.

The following visits and procedures will occur during the Treatment Phase:

Blood Draw Visit B (7.5 month): Approximately 15 minutes for blood draw

TSH and T4 blood draw will be done 6 weeks after the 6 month visit (at 7.5 months) as a measure of efficacy of levothyroxine dose.

Study Visit #3 (12 month) = 1 visit lasting approximately 4 hours

- Fasting blood draw: 15 minutes
- Pubertal Status Exam: 5 minutes
- Vital Signs: 10 minutes
- DXA scan: 10 minutes
- Anthropometric measurements: 15 minutes
- Family history: 10 minutes
- Questionnaire assessments (PedsQL, IWQOL, BES, FRS, ASAQ, CEBQ, CFQ, ABAS-II, HFI): 1.5 hours, or as long as needed by subject and parent/guardian. HFI will be mailed to family and completed prior to visit.
- Physical activity armband (worn at home for 7 days)
- 3 day dietary recalls over the phone from home = Approximately 30 minutes for each diet recall.

Blood Draw Visit C (13.5 month): Approximately 15 minutes for blood draw

TSH and T4 blood draw will be done 6 weeks after the 12 month visit (at 13.5 months) as a measure of efficacy of levothyroxine dose.

Study Visit #4 (18 month) = 1 visit lasting approximately 4 hours

- Fasting blood draw: 15 minutes
- Pubertal Status Exam: 5 minutes
- Vital Signs: 10 minutes
- DXA scan: 10 minutes
- Anthropometric measurements: 15 minutes
- Family history: 10 minutes
- Questionnaire assessments ((PedsQL, IWQOL, BES, FRS, ASAQ, CEBQ, CFQ, ABAS-II, HFI): 1.5 hours, or as long as needed by subject and parent/guardian. HFI will be mailed to family and completed prior to visit.
- Physical activity armband (worn at home for 7 days)
- 3 day dietary recalls over the phone from home = Approximately 30 minutes for each diet recall.

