3 INVESTIGATIONAL PLAN

3.1 General Schema of Study Design

This randomized, single-blinded, intervention study will take place at the CHOP outpatient CTSC and at Children's National Medical Center. Subjects with Down syndrome and subclinical hypothyroidism (TSH: 5-10 mIU/L) ages 8-20 years will be recruited for a trial of levothyroxine treatment, using a switching replication design. All subjects will be observed for 6 months. TSH and T4 will be obtained at the 3rd and 6th month of the observation period. If a subject has a TSH which has reverted to normal at 3 months, they will continue on to the 6-month check. Only subjects with persistently elevated TSH (5-10 mIU/mL) at 6 months will be enrolled in the randomized phase. While there is no standard definition of "persistently elevated," in this study, we consider TSH level that is 5-10 mIU/L at 0 and 6 months as "persistently elevated." If TSH is < 5 mIU/L at 0 months and the subject has a history of TSH 5-10 mIU/L, a repeat TSH may be drawn, at the discretion of the principle investigator, within 3-6 months; if TSH is < 5 mIU/mL at 6 months, a repeat TSH may be drawn, at the discretion of the investigator, within 1-2 weeks. If the repeat TSH is < 5 mIU/L, the subject will not be eligible to continue. If TSH is > 10 mIU/L during the first 6 months, a repeat TSH will be drawn within 1-2 weeks. If the repeat TSH is > 10 mIU/L, thyroid dysfunction will not be considered subclinical. The subject will be referred to an endocrinologist for definitive therapy. After 6 months of observation, subjects will be randomized to: Group 1 (6 months of placebo, followed by 6 months of levothyroxine) or Group 2 (12 months of levothyroxine). The initial levothyroxine dose will be 0.5 – 1 mcg/kg/day, with a goal of TSH desired range of 0.5 – 3 mIU/L. Subjects/families will be blinded to the treatment arm. Investigators will be unblinded to permit titration of levothyroxine dose. TSH and T4 will be measured after 6 weeks (month 7.5) of levothyroxine/placebo commencement (as a measure of efficacy of levothyroxine dose), and then at month 12. At month 12, levothyroxine will be initiated in Group 1 (delayed treatment), allowing for 6 months of treatment. Group 2 (immediate treatment) will continue an additional 6 months of levothyroxine (12 months total). TSH will be checked at 6 weeks (month 13.5) and at month 18 in both groups. Dose adjustments will be made at the discretion of the PI. TSH will be repeated 6 weeks after any dose adjustments, which may be in addition to the time points above if necessary. This switching replication design will permit using each child to serve as his/her own control and provides a placebo control period for each treated child. The goal is for 20 subjects to complete the 18 month study.

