3.1.2 Observation Phase

The first 6 months of the study are the Observation Phase of the study. Only subjects with persistently elevated TSH during the Observation Phase will proceed to the Treatment Phase. Subjects that have TSH >10 mIU/L during the 6 month Observational Phase will have a repeat TSH test within 1-2 weeks. If the repeat TSH is >10 mIU/mL, the subject not be considered to have subclinical hypothyroidism and will not qualify to continue the study. They will be referred to an endocrinologist for treatment. Subjects who have TSH <5 mIU/L at the 6 month visit may have a repeat TSH test within 1-2 weeks; this will be at the discretion of the study investigator. If TSH or repeat TSH (if applicable) is <5 mIU/L, the subject will be considered to have normal levels of TSH and will not qualify to continue the study. Subjects who have a history of subclinical hypothyroidism, but at the 0 month visit have a TSH value in the normal range, may have a repeat TSH test within 3-6 months; this will also be at the discretion of the study investigator.

Study Visit #1 (0 Month):- For subjects recruited from #9233, #9233 data will serve as Study Visit #1 data. Study visit #1 will not be necessary for subjects recruited from #9233.

Subjects who have not participated in Study #9233 will complete Study Visit #1. Subjects and their parents/guardians will come to the research facility following a 12 hour overnight fast. Parental/guardian/Legal Authorized Representative consent and child assent (if child is deemed capable of assent) will be obtained prior to any study procedures being performed. Females will receive a urine pregnancy test. Females found to be pregnant will be disqualified from the study and will receive appropriate counseling and referral. Study participants will have the following measures: fasting blood samples, TSH, T4, anthropometric measurements, whole body DXA scan, blood pressure, pubertal assessment, pulse wave velocity & pulse wave analysis, echocardiography and questionnaire assessments. After the study visit, subjects will be asked to wear a physical activity arm band at home for 7 days, and a 3 day dietary recall will be done by telephone.

Blood Draw Visit A(3 Month):- During this observation time frame, subjects will have a blood draw to check TSH and T4 levels. This blood draw can be done at the research facility or at other hospital-affiliated sites.

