9.1.2 Blinding

Subjects/families will be blinded to treatment arm. Investigators will not be blinded to permit titration of levothyroxine dose.

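### Unblinded investigators decide case by case who gets a repeat TSH at the month-6 gate, so under blocked allocation the entry of borderline subjects could depend on the likely next arm; the entry rule is also worded inconsistently

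*Combined protocol and SAP*

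**What the plan says.** **Allocation.** Under section 4.3.1 (and 3.2 in near-identical terms) the project statisticians randomize centrally, and the allocation is "implemented using opaque sealed envelopes to ensure allocation concealment". Balance is kept by "randomly permuted blocks with unequal block sizes and with stratification by patient gender" and age, for two groups of 10. Block sizes are not given. Nor does the plan say who holds and opens the envelopes, or whether they are divided between the two sites.

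**Blinding.** Section 9.1.2: "Investigators will not be blinded to permit titration of levothyroxine dose". Sections 1.2 and 3.1 agree. Investigators therefore know the arm of each subject already randomized.

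**Month-6 gate.** Section 3.1.2: "Subjects who have TSH <5 mIU/L at the 6 month visit may have a repeat TSH test within 1-2 weeks", at the investigator's discretion. Sections 3.1 and 6.3 allow the same. A value above 10 during observation, by contrast, must be repeated; no discretion is given.

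**Definition of persistence.** Section 3.1: "we consider TSH level that is 5-10 mIU/L at 0 and 6 months as" persistently elevated. For a subject with a history of raised TSH whose month-0 value is below 5, the same section says "a repeat TSH may be drawn, at the discretion of the principle investigator, within 3-6 months". Section 4.2.1 adds that the PI may order further draws after the month-0 and month-6 visits, with no stated limit.

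**The concern.** Allocation concealment should ensure that the decision to admit a subject cannot depend on the arm that subject will receive. Three features together leave a gap: blocked assignment, which makes the next arm partly predictable from past ones; investigators who know the past ones; and an entry decision left to those investigators. No section requires eligibility to be recorded as final before an assignment is released.

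If the repeat were offered more readily when a particular arm seemed due, the arms could differ at entry in ways that randomization is meant to prevent. With 10 per arm, one subject is 10% of an arm. The comparison most exposed is placebo against levothyroxine over months 6 to 12, the only period in which the arms receive different treatment.

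Separately, the sections that define who may be randomized do not agree. Even a scrupulous investigator cannot tell from the text whether a reading below 5 followed by one in range qualifies.

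**Working it through.** The plan gives no figure for predictability or for the number of subjects near the threshold, so there is none to reproduce. The power table in section 6.2 does not bear on this point.

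**1. How guessable is the next arm?** From the plan: 20 randomized 1:1, four sex-by-age strata (average 20/4 = 5), permuted blocks of varying size. Assumed: the block sizes, each equally likely; a guesser who knows every earlier assignment in the stratum and picks the arm with fewer subjects so far. Simulation, with stratum sizes varying at random:

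| Assumed block sizes | Four strata | One unstratified list | Separate lists by site (8 cells) | Known with certainty, of 20 (four strata) |
|---|---|---|---|---|
| {2,4} | 69% | 72% | 66% | 1.65 |
| {2,4,6} | 66% | 70% | 63% | 0.42 |
| {4,6} | 65% | 69% | 60% | 0.94 |

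Hand check for {2,4} with exactly five in a stratum: the chances of a correct guess for subjects 1 to 5 are 1/2, 5/6, 7/12, 11/12 and 13/24. They sum to 81/24 = 3.375, and 3.375/5 = 67.5%. The simulation for exactly five gave 3.376. On that basis the three schemes give 64-68%.

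The strata are not the cause: one list with the same blocks is slightly more guessable. Varying the block size does help. Fixed blocks of 4 and of 2 would make 5.0 and 9.0 of 20 assignments certain.

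**2. How much does the repeat decision matter for one subject?** Assumed: within-subject TSH CV of 15-30% (not in the documents), normal and independent readings. For true mean m, p = P(reading at least 5) = 1 - Φ((5 - m)/(CV × m)). With m = 4.5 and CV 20%: (5 - 4.5)/0.9 = 0.556, so p = 0.289. Over CV 15-30%, p = 0.23-0.36. After a first reading below 5, the decision to repeat thus moves the chance of passing month 6 from 0 to about 0.23-0.36, if the repeat is allowed to count. Before either reading, the chance of passing with a repeat always given is 1 - (1 - p)², or 0.41-0.59.

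That concerns the month-6 gate only. The subject must also pass month 0. With no month-0 repeat and CV 20%, the overall chance rises from 0.289 × 0.289 = 0.08 to 0.289 × 0.495 = 0.14.

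**3. What could steering achieve?** If k of the 20 entered through a discretionary repeat, and every such decision followed the guess, the excess in the guessed arm is k × (guess rate - 0.5). For k = 2 to 6 (assumed) and rates of 65-69%: 2 × 0.15 = 0.3 up to 6 × 0.19 = 1.1 subjects. The ceiling, if all 20 could be steered, is 20 × 0.15 = 3.0 to 20 × 0.19 = 3.8. It is not realistic, because only values below 5 are discretionary.

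**4. The entry rule, side by side.**

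| Section | Rule |
|---|---|
| 3.1, definition | 5-10 at both month 0 and month 6 |
| 3.1, repeats | a normal month-0 or month-6 value may be repeated; only a repeat below 5 is named as disqualifying |
| 3.1.2 and 6.3 | the TSH, or the repeat if there is one, being below 5 disqualifies |
| 9.1.1 | above 5 at month 6, no upper limit |

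The wording in 3.1.2 and 6.3 has two readings. If either value below 5 disqualifies, the repeat can never change the outcome. If the repeat replaces the first value, they agree with 3.1. The plan also does not say whether a month-0 repeat, which may come as late as month 6, replaces the month-0 value or restarts the six-month clock.

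**The case against.** The case for the plan is substantial. The list is generated centrally, block sizes vary, and Table 1 shows randomization as a separate no-visit step after Study Visit #2. Fewer than 2 of 20 assignments would be certain. The 65-69% supposes a guesser who tracks every earlier assignment in the stratum. Motive is limited: both arms receive levothyroxine during the trial. Section 9.4.1 says lipids are run in batches and may be reported late, so non-HDL-C, the primary outcome, may not be known when the repeat is decided. The key contrasts in sections 6.1.1 and 6.1.2 are before against after treatment, which arm-selective entry affects less. All of this stands and limits the size. It does not close the route, because discretion and knowledge of past assignments remain with the investigators.

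A reader might infer more than the documents support:

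- *That envelopes or small strata are at fault.* Envelope custody is unstated, not shown to lie with recruiters, and removing the strata would not lower the guess rate. Central release with the same blocks would leave it at 65-69%.
- *That retesting is one-sided.* Values above 10 are also repeated. The asymmetry is that only the lower-side repeat is discretionary.
- *That the plan admits subjects who fail its own definition.* That is one reading of section 3.1. A literal reading of 3.1.2 and 6.3 excludes them, and a repeat that replaces the scheduled value would satisfy the definition.
- *That the treatment effect is diluted.* The documents give no basis for sizing this.

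**Conclusion.** The point holds as a limited vulnerability. Unblinded, discretionary gatekeeping combined with blocked assignment lets a guess about the next arm influence whether a borderline subject enters. The guess is right about 65-69% of the time under the assumed block sizes (60-66% if lists are kept separately by site), against 50% by chance. Only subjects below 5 at month 6 are exposed, and the consequence falls mainly on the month 6-12 between-arm comparison. The number of such subjects, and hence any bias, is not established. The 0.3 to 1.1 subjects above rests on assumed counts and on every decision following the guess. Nothing shows that selection occurred or would occur.

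The inconsistency in the entry rule needs none of these assumptions and should be resolved in any case.

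**What to change.** 1. Replace the discretionary month-6 repeat by one pre-specified rule applied identically to every subject, or give the decision to someone unaware of earlier assignments. This is the step that removes the route.
2. Record eligibility, including any repeat TSH, as final in REDCap before the statistician or the CHOP Investigational Pharmacy releases the assignment. This step alone would not prevent a guess from influencing the earlier decision, but it makes the order auditable.
3. Reconcile sections 3.1, 3.1.2, 6.3 and 9.1.1, together with the open-ended extra draws in 4.2.1. State whether a repeat replaces the scheduled value at month 0 and at month 6. Which TSH rule is right is for the sponsor.
4. State who holds and opens the envelopes, if they are kept. In the same edit, place age 14 in one stratum: "two strata, ages 8-14 and ages 14-20" covers it twice.

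Blocking need not be dropped. Simple randomization would bring the guess rate to 50%, but at N = 20 it carries a 26% chance of a 13/7 split or worse.

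The cost is protocol wording. The list is already central, randomization needs no visit, and the pharmacy and REDCap are in place. The downside is a few more repeat draws if everyone below 5 is retested, or a few fewer qualifying subjects if no one is.

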4.4 Blood Draw Visits B & C

Randomized subjects will be asked to have a blood draw to check TSH and T4 levels 6 weeks after the 6 month and 12 month visits. TSH will be repeated 6 weeks after any dose adjustment. The purpose to for this check is to adjust the levothyroxine dose if the PI deems necessary.

4.5 Concomitant Medication

After the participant has completed the screening and interim visits, the participant will be randomized to take an oral placebo or levothyroxine treatment. The initial levothyroxine dose will be 0.5-1 mcg/kg/day. Participants are required to bring in their full or partially full bottles of placebo/levothyroxine to each study visit (Study Visits #3 and 4). Subjects can continue other medications; these will be recorded at each study visit.

4.6 Subject Completion/Withdrawal

Subjects may withdraw from the study at any time without prejudice to their care. They may also be discontinued from the study at the discretion of the Investigator for lack of adherence to study treatment, visit schedules, or AEs. The Investigator or the Sponsor (if applicable) may also withdraw subjects who violate the study plan, or to protect the subject for reasons of safety or for administrative reasons. It will be documented whether or not each subject completes the clinical study. If the Investigator becomes aware of any serious, related adverse events after the subject completes or withdraws from the study, they will be recorded in the source documents and on the CRF.

5 STUDY EVALUATIONS AND MEASUREMENTS

5.1 Screening and Monitoring Evaluations and Measurements

- Fasting blood draw: This will be completed by nursing staff. A total of approximately 12.5 mL (approximately 2½ teaspoons) of blood will be obtained.
 - Pubertal Status Exam: Tanner staging of puberty will be performed by a pediatric endocrinologist team member. This exam will take place in a private exam room.
 - Vital Signs: Blood pressure, heart rate, and respiratory rate will be taken by the nursing staff. The blood pressure will be taken 3 times and averaged. Vital signs will be collected after the blood draw.
 - Full Body DXA Scan: The DXA scan will be performed by trained . The scan measures BMC, BMD, BMD-Z, fat mass, lean body mass, total mass, fat-free mass and percent fat.
 - Anthropometry: Weight will be measured by digital electronic scale (Scaletronix) and stature on a stadiometer (Holtain). Body proportions and fat distribution measurements (sitting height, arm and waist circumference, and skin fold thickness at triceps, biceps, subscapular, and suprailiac sites) will be measured.
 - Pulse Wave Velocity (PWV) and Pulse Wave Analysis (PWA): Aortic PWV and PWA will be measured by a trained technician. PWV and PWA will only be done at Study Visit #1.
 - Echocardiography: LV mass will be measured by echocardiography by a trained technician. Echocardiography will only be done at Study Visit #1.
 - Family History: The study coordinator/appropriate member of the investigative team will administer the CRF to collect relevant patient medical history, family history of CVD/dyslipidemia/T2DM.
 - Questionnaire Assessments: The following questionnaires: (PedsQL, IWQOL, BES, FRS, ASAQ, CEBQ, CFQ, ABAS-II, body satisfaction scales) will be administered by the study coordinator/appropriate member of the investigative team. Each questionnaire will be verbally communicated to the parent/participant, and the team member will show the questions as they are read, as appropriate. The HFI and physical activity/armband diary will be self-administered at home.
 - PedsQL - The Pediatric Quality of Life Inventory uses a modular approach to measuring health related QOL in healthy children, adolescents, and those with acute and chronic health conditions. Scales include: 1) physical functioning, 2) emotional functioning, 3) social
-

functioning, and 4) school functioning, which yield summary scores of a total scale score, a psychosocial health summary score, and the physical health summary score.

- IWQOL-Kids - The Impact of Weight on Quality of Life – Kids (IWQOL-Kids) © is a validated self-report measure of weight-related quality of life for youth ages 11-19. This condition-specific QOL assessment is a 27 item questionnaire that yields a total score and 4 domain scores, including physical comfort, body esteem, social life, and family relations. It has been used in children, adolescents, and in special populations.
 - IWQOL-Kids – Parent Form - The Impact of Weight on Quality of Life Kids – Parent Form (IWQOL-Parents) is a measure of the parent perception of weight-related quality of life. This condition-specific QOL assessment is a 27 item questionnaire that yields a total score and 4 domain scores, including physical comfort, body esteem, social life, and family relations.
 - BES – the Body Esteem Scale for Children is a 20-item, yes/no questionnaire designed to assess children’s attitudes and feelings about their body and appearance.
 - FRS – The Stunkard Figure Rating Scale depicts 9 male and 9 female figures, ranging in size from very thin to very overweight. It is used to assess perceptions of current and ideal body size.
 - ASAQ - The Adolescent Sedentary Activity Questionnaire is a reliable assessment of a comprehensive range of sedentary behaviors that occur in school-aged young people. In this measure, the parent will estimate the amount of time spent engaging in various sedentary activities during each day of a typical school week and weekend.
 - CEBQ – The Child Eating Behavior Questionnaire is a reliable and valid, 35 item questionnaire measuring appetite and eating style (satiety responsiveness, food enjoyment, food responsiveness, slowness in eating, food fussiness, desire to drink, emotional over-eating and emotional under-eating).
 - CFQ – The Child Feeding Questionnaire measures parental feeding practices, assessing parental beliefs, attitudes, and practices regarding child feeding. It is designed for parents of children in the age range of 2-11 years of age.
-

-
- ABAS-II – The Adaptive Behavior Assessment System-Second Edition is widely used to evaluate individuals with intellectual and developmental disabilities measuring daily living skills (what people actually do, or can do, without the assistance of others). It assesses adaptive behavior in individuals 5-21 years of age.
 - Body Satisfaction Scales – The body satisfaction scales measure the level of satisfaction with body size, shape and weight.
 - HFI – The Home Food Inventory is a valid assessment of the home food environment. Families will be mailed the HFI prior to the study appointment and will be asked to bring the completed survey to the study appointment.
 - Physical activity/armband diary – Participants will be asked to keep a record of the times that they did not wear the physical activity armband and of their activities on the days that they wore the armband. The diary packet will be sent home with each participant, along with a postage-paid envelope to return the diary.
 - Sense Wear® Armbands (Body Media, Inc): Participants will pick up the Sense Wear armbands at the visit. The subject will be asked to wear the armband accelerometer for 7 consecutive days, 24 hours per day. The exception of wearing the armband is when the subject is bathing/showering or if participating in water activities, such as swimming. Information collected will include the amount and intensity of physical/sedentary activities and sleep.
 - 3 day dietary recalls: After the study visit, a nutritionist will contact the participant and guardian by phone to collect information as to what the participant ate and drank within the last 24 hours. This will be done three times (2 weekdays and 1 weekday).

